1 INTRODUCTION

The primary aim of this project is to create an online weight management tool (Physical activity, weight management and cognitive behavioural therapy) to prevent significant weight gain following kidney transplantation. Designing the online interactive weight management resource for kidney transplant patients will involve patient and health care professional input through Qualitative methodology such as ‘Think-Aloud’ interviews and one-to-one semi-structured interviews. This online resource will be called “exertion” and will be created by the research team, with technical support from the SPIKA Software Company.

Results from this study will refine the resource, and lead to a study application for a randomised controlled feasibility trial where we plan to test the “exertion” online application. Therefore this project has potential to influence clinical practice for kidney transplant recipients. It will allow patients, who may not have routine access to physio or dietetic input to address weight gain with support. A study flow chart summarising the project can be found below.

1.1 STUDY FLOW DIAGRAM ExeRTiOn

[figure not shown]

Figure 1. Study flow diagram.

2 BACKGROUND AND RATIONALE

Physical activity and exercise play a beneficial role in maintaining the health of those with chronic illnesses however poor physical functioning among patients with chronic kidney disease (CKD) is well recognised (1, 2). Kidney Transplantation (KTx) is an effective treatment option for life threatening end-stage kidney disease and becomes cost-effective over the average lifespan of the transplant, although it is not without associated risk. The use of modern immunosuppression therapies have improved the life-expectancy of the kidney graft; however, there is a high prevalence of diabetes, cardiovascular disease and obesity (3, 4). It has been established that recipients of KTx increase their physical activity level in the subsequent years after transplantation due to improved quality of life; however, within that time they do not reach the level of physical activity of those of age-matched healthy controls (5). A reason for this is that despite the reversal of many of the prevailing uraemic symptoms following KTx, functional capacity remains compromised due to a combination of prior deconditioning, uraemic myopathy, muscle atrophy and muscle pathology as a result of immunosuppression therapy (6, 7).

Weight gain is a significant and real issue for kidney transplant recipients (8, 9). Obesity remains a widespread issue for KTx recipients with an estimated two thirds of the population being overweight or obese (8). Research suggests that patients who gain more than 15% of their initial weight during the first year after receiving a kidney transplant, they have a higher chance of dying from conditions not related to their kidney function within ten years (9). Although weight gain and maintaining a programme of activity are real concerns for KTx recipients, they are not routinely offered specialist physical activity or weight management programmes in the UK. There are some community schemes for exercise and weight management available. However kidney transplant patients report they are not always understanding of the specific issues surrounding kidney transplantation. Extra appointments, travel time, and return to work where highlighted as barriers to participate in our supervised kidney transplant study (10). Robust research reviews suggest that online behavioural weight management interventions can help people regulate food intake and activity, and on average can lead to clinically meaningful weight loss (11, 12). Therefore there is a need to create an online weight management and physical activity tool, specific to KTx recipients, imbedded with cognitive behavioural therapy and motivational interviewing methods to address post-transplant weight gain. I would like to create this app with input from the research team, kidney transplant patients, and health care professionals (HCP's) working in the transplant team at a South London Teaching Hospital.

2.1 Primary Objective

To create a patient focused online weight management and physical activity tool for new transplant recipients called “exertion”.

2.2 Secondary Objectives

a) To explore the current themes through qualitative data collection:

- Components of the “exertion” resource that are helpful/ unhelpful
- Any difficulties/ barriers to using the “exertion” application

- Any difficulties/ barriers to participating in the study?
- Strengths of the “exertion” resource
- Weaknesses of the resource
- Patient experience and learning using the online resource
- Transplant health care professional experience and knowledge reviewing the online resource

3 STUDY DESIGN

This study is a qualitative study and intervention planning study to create and refine an online resource for weight management in new kidney transplant recipients, which will be named “exertion”.

3.1 Objectives and hypothesis:

The aim of this qualitative study is to use qualitative methods to create and refine a weight management, exercise/ physical activity online resource for patients with kidney transplant recipients.

This study involves data collection via:

- Think-aloud interviews- 5 KTx patients and 2 HCP working in the transplant team will have recorded think aloud interviews using the resources. Other participants will be exposed to the resource during a routine lab session.
- Semi-structured interviews of transplant HCP’s and KTx recipients.
- Demographic data including age, gender, occupation, smoking history, medical history, medication lists and baseline body weight (kg).
- Website/ resource log in data
- Field notes and observations from Think Aloud interviews, lab sessions and semi-structured interviews

We aim to recruit 10 new kidney transplant recipients and 5 transplant health care professionals to explore the following themes through ‘Think-Aloud’ interviews:

- The functionality of the “exertion” online resource for KTx recipients
- The functionality of the “exertion” online resource from a HCP perspective
- KTx participants interpretation of the “exertion” modules and resource as a whole
- HCP participants interpretation of the “exertion” modules and resource as a whole
- Thought processes involved to use the “exertion” application
- Recommendations from participants
 - Likes/dislikes
 - Barriers/ easier to use sections
- Highlight individual differences in the use of the “exertion” resource

We aim to explore the following themes through semi-structured individual interviews and focus groups:

- What components of the online resource (exertion) are helpful/ unhelpful from a kidney transplant perspective
- What components of the online resource are helpful/unhelpful from a kidney transplant HCP perspective
- Are there any difficulties/ barriers participating in the study?
 - And are they what were expected or different?
- Patients experiences and learning using the online application, and when the changes were noticed
- Anything missing/ they would recommend adding to the application.

Trial duration per participant: One study visit.

Estimated total trial duration: 9 months in total to create resource and have it reviewed by patients and health professionals (3 months to create, 3 months to test and 3 months to refine).

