3.2 The “exertion” Online Resource

The “exertion” (exercise in renal transplant online) resource will be created by the research team, including physiotherapists and dietitians working in renal specific weight management, with technical software support from SPIKA Company. This is a single centre study at King’s College Hospital recruiting 10 kidney transplant recipients and 5 health care professionals from the transplant clinical team. As this study will involve patient interviews and qualitative data, ethical approval will be sought.

The resource will include individually tailored physical activity (PA) (e.g.: walking and cycling), recorded using a pedometer or smart phone apps. PA will be based on current guidelines recommending a minimal amount of 1000 kcal/week expended for health benefits, with optimal benefits associated with 1500-2000kcal/ week. Dietary information from the existing weight management programme at King’s College Hospital (KCH) will be accessible to the patients online, including resources like “managing cravings”, “goal setting” and “problem solving”. The intervention will involve monthly web-based sessions that will start at 6 weeks post transplantation and continue until 12 months post-transplant surgery. For the purpose of this current study, participants will only have access to the online application in a one of session to review and refine the resource. It is clinical practice at our centre for KTx recipients to be cleared to resume structured physical activity post ureteric stent removal which occurs approximately 6 weeks post-surgery.

The packages will focus on modelling prescribed PA and healthy eating advice, and will involve cognitive behavioural techniques to support behavioural change. Recognised behavioural change techniques will be used which will include goal setting, evaluating outcome expectancies and values, self-regulation action planning), and behaviour monitoring will form the core principles. The sessions will also aim to increase treatment self-efficacy

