(physical activity) and reduce fear avoidance (using basic acceptance and commitment therapy principles). Tailored feedback will include encouragement and virtual rewards if maintaining weight. Weight gain will trigger initial referral to an automated recovery package. This package will be built into the interventional platform and automatically activate given an increase in weight. The nature of this package is to ensure that following weight gain, the patient remains engaged with this interventional programme and will provide additional behavioural support. The online tool will be accessible either online, or via a smart phone or tablet as a health application (app).

We plan for the resource to allow participants to select modules to work through on a monthly basis over a 12 month period. Behavioural change tools and resources will be embedded within the “exertion” resource. For this current study, participants will access the online exertion resource at a one off supervised research visit. Participants will not have exposure or access to this online resource outside this study visit. The main modules will include information and interactive text on the following areas:

1. Managing cravings and prednisolone
2. Goal setting for activity and food planning
3. Portion sizes and the NHS healthy plate
4. Patient examples of strategies to plan activity (physical activity planning)
5. Patient examples of strategies to eating out/ holidays with low fat diets (food planning)
6. Reading food labels and making healthy food choices
7. Identifying barriers
8. Problem solving
9. Relapse prevention
10. Planning for the future

To ensure the modules are interactive, participants will be asked questions relating to:

- Number of steps and self-reported physical activity levels
- Weight, height, BMI
- Portion sizes
- Individual SMART goals regarding food and activity. The participants will be asked if they have achieved these set goals.
- Problem solving questions for activity and food
- Rating the importance and confidence in ability to make changes to food an activity using a VAS (visual analogue scale)

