4 STUDY SCHEDULE

Assessments:

After written consent is received, participant's demographic baseline information at entrance to the trial will be recorded. 5 of the KTx recipients and 2 of the HCP will undergo 'Think-aloud' interviews to assess the usability of the exertion resource. Usability is defined as how

easily someone can use and interact with the online system without any formal training (13). ‘Think-Aloud’ interviews are a qualitative research technique that assesses how the user interacts with the system and a sample of five can uncover 80% of usability problems and issues (13). ‘Think-aloud’ interviews provide a valid source of data concerning participant thinking as the participant is asked to vocalise as they perform a task, supervised by the researcher (14). Therefore in this study, the main researcher will record verbatim from participants as they talk out loud whilst accessing and using the exertion resource. The researcher will also record field observation notes during the think aloud interviews. Verbal speech and site log in data will be recorded from these sessions. We estimate these interviews will take 60-90 minutes.

The remaining participants (5 KTx and 3 HCP), will have the same amount of time reviewing the resource at the start of the session (60-90 minutes). After the ‘Think-aloud’ interviews or review of resources, participants will complete a one-on-one semi-structured interview to review their thoughts and experiences on using the exertion resource. Please refer to summary of study flow diagram on page 5 and schedule of assessment (Table 1) below. Having the semi-structured interviews on the same day as the ‘Think-aloud’ interviews or the reviewing of the resource will minimise patient burden and recall bias.

Table 1- Schedule of Assessment

Procedure	Recruitment	Visit 1
Screening and informed written consent	X	
Medical history and demographics		X
‘Think-Aloud’ interviews: - 5 KTx - 2 HCP - Estimate 60-90 minutes total		X
Exposure to the resource lab sessions Estimate 60-90minutes total		X
Semi structured individual interviews (n=9 KTx, n=5 HCP)		X

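### Can patients say when they noticed changes if they use the resource once and are interviewed the same day?

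*Combined protocol and SAP*

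**What the plan says.** Section 3.1 sets out five main themes for the semi-structured interviews. The fourth is "Patients experiences and learning using the online application, and when the changes were noticed". The changes are not defined there or elsewhere. The section closes with "Trial duration per participant: One study visit".

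The rest of the plan fixes how much use comes before the interview:

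- Section 3.2 states that "participants will only have access to the online application in a one of session to review and refine the resource", and later that "Participants will not have exposure or access to this online resource outside this study visit".
- Section 4 says of the think-aloud sessions, "We estimate these interviews will take 60-90 minutes". The remaining participants get the same time to review the resource.
- Section 4 places the semi-structured interview on the same day for both groups, to limit patient burden and recall bias. Table 1 has two columns only, recruitment and Visit 1.

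The corresponding secondary objective in section 2.2 reads "Patient experience and learning using the online resource". It does not mention the timing of changes.

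**The concern.** A question about when changes were noticed presupposes that the person has used the resource for long enough to change. The full programme described in section 3.2 would allow that, with monthly sessions from 6 weeks to 12 months after transplant. Participants in this study do not receive it. They see the resource once and are interviewed within hours.

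If the clause went unchanged into the topic guide, patients less than three months after transplant (section 6.1.1) could answer in two unhelpful ways. They might say what they expect to change, or describe changes since surgery that have nothing to do with the resource. Section 1 says the results will refine the resource and lead to an application for a randomised feasibility trial. The worry is that such answers might be taken there as experienced effects.

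**Working it through.** No power, alpha or sample-size figure bears on this point. The check sets the theme beside the schedule and then asks what depends on it.

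**1. Exposure before the interview.** Sections 3.2 and 4 give 1 session of 60-90 minutes, which is 60/60 = 1.0 to 90/60 = 1.5 hours. There is no period of use between that session and the interview. The planned programme runs from week 6 to month 12, roughly 52 - 6 = 46 weeks, and none of it is delivered here.

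**2. What the changes could mean.**

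| Reading | Answerable under this design? |
|---|---|
| Change in weight, diet or activity caused by the resource | No. There is no period of use, and body weight is listed at baseline only (section 3.1). |
| Shift in understanding or confidence during the session | Yes. The theme is about experiences and learning, the modules ask users to rate importance and confidence on a visual analogue scale (section 3.2), and the think-aloud sessions record speech, field notes and log-in data throughout (section 4). |
| Change since the transplant | Patients could answer, but the answer would not concern the resource. |

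The obstacle in the first row is the lack of any use before the interview. It is not the lack of a second visit: one retrospective interview can date a change if a period of use came first.

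**3. How much of the plan is touched.** The clause is in 1 of 5 main semi-structured themes, and the rest of that theme remains answerable. It concerns the patient interviews only (9 in Table 1; 10 patients recruited in section 6.1).

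**4. What depends on the clause.**

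- *Sample size (section 8.1):* five patient and two staff think-aloud interviews, supported by the share of usability problems found with five, plus individual interviews to data saturation. Neither uses the timing of changes.
- *Analysis (section 8.2):* summary statistics for baseline demographics, and inductive thematic analysis of the interviews. No step dates a change or estimates an effect.
- *Objective (section 2.2):* experience and learning, with no timing element.
- *Questions actually asked (section 8.1):* topic guides still to be developed and discussed with the patient advisory group and the steering group.

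Dropping the clause would leave every item in this list as it is.

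**The case for a change.** The best case for acting is that the mismatch is real and costs almost nothing to remove. Section 3.1 is the natural source for the topic guides. The reading about learning within the session is partly redundant, since the same line already covers experiences and learning. Even if a narrower meaning was intended, it is not stated. Deleting a few words would bring section 3.1 into line with section 2.2 and close off the risk that changes since transplant are credited to the resource.

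Most of this stands as a comment on wording. The clause is loose, and on its natural reading it cannot be answered from one session. The consequence does not follow, however. Harm needs two further steps: the clause must pass unaltered through guide development and discussion with two groups, and the answers must then be reported as effects of use. Nothing in the plan provides for the second step. Analysts would also know that each participant had one supervised session, so they have what they need to read an answer about change as anticipated, within the session, or unrelated to the resource. The single-visit design is deliberate, with its reasons given in section 4, and is not at fault.

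**Conclusion.** The mismatch exists but calls for no change to the plan. Changes in weight, diet or activity from using the resource cannot be noticed or dated after 60-90 minutes of use and a same-day interview. Shifts in understanding or confidence can be discussed, and the plan does not say which kind it means. The clause affects part of one theme in five, and no objective, sample size, analysis or stated refinement decision rests on it. Removing it would be editorial and would alter no result.

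This conclusion assumes that the study flow diagram, which is not reproduced in the text available, adds no later contact with participants; Table 1 shows none. It also assumes that the topic guides are developed and discussed as section 8.1 describes.

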3.2 The “exertion” Online Resource

The “exertion” (exercise in renal transplant online) resource will be created by the research team, including physiotherapists and dietitians working in renal specific weight management, with technical software support from SPIKA Company. This is a single centre study at King’s College Hospital recruiting 10 kidney transplant recipients and 5 health care professionals from the transplant clinical team. As this study will involve patient interviews and qualitative data, ethical approval will be sought.

The resource will include individually tailored physical activity (PA) (e.g.: walking and cycling), recorded using a pedometer or smart phone apps. PA will be based on current guidelines recommending a minimal amount of 1000 kcal/week expended for health benefits, with optimal benefits associated with 1500-2000kcal/ week. Dietary information from the existing weight management programme at King’s College Hospital (KCH) will be accessible to the patients online, including resources like “managing cravings”, “goal setting” and “problem solving”. The intervention will involve monthly web-based sessions that will start at 6 weeks post transplantation and continue until 12 months post-transplant surgery. For the purpose of this current study, participants will only have access to the online application in a one of session to review and refine the resource. It is clinical practice at our centre for KTx recipients to be cleared to resume structured physical activity post ureteric stent removal which occurs approximately 6 weeks post-surgery.

The packages will focus on modelling prescribed PA and healthy eating advice, and will involve cognitive behavioural techniques to support behavioural change. Recognised behavioural change techniques will be used which will include goal setting, evaluating outcome expectancies and values, self-regulation action planning), and behaviour monitoring will form the core principles. The sessions will also aim to increase treatment self-efficacy

(physical activity) and reduce fear avoidance (using basic acceptance and commitment therapy principles). Tailored feedback will include encouragement and virtual rewards if maintaining weight. Weight gain will trigger initial referral to an automated recovery package. This package will be built into the interventional platform and automatically activate given an increase in weight. The nature of this package is to ensure that following weight gain, the patient remains engaged with this interventional programme and will provide additional behavioural support. The online tool will be accessible either online, or via a smart phone or tablet as a health application (app).

We plan for the resource to allow participants to select modules to work through on a monthly basis over a 12 month period. Behavioural change tools and resources will be embedded within the “exertion” resource. For this current study, participants will access the online exertion resource at a one off supervised research visit. Participants will not have exposure or access to this online resource outside this study visit. The main modules will include information and interactive text on the following areas:

1. Managing cravings and prednisolone
2. Goal setting for activity and food planning
3. Portion sizes and the NHS healthy plate
4. Patient examples of strategies to plan activity (physical activity planning)
5. Patient examples of strategies to eating out/ holidays with low fat diets (food planning)
6. Reading food labels and making healthy food choices
7. Identifying barriers
8. Problem solving
9. Relapse prevention
10. Planning for the future

To ensure the modules are interactive, participants will be asked questions relating to:

- Number of steps and self-reported physical activity levels
- Weight, height, BMI
- Portion sizes
- Individual SMART goals regarding food and activity. The participants will be asked if they have achieved these set goals.
- Problem solving questions for activity and food
- Rating the importance and confidence in ability to make changes to food an activity using a VAS (visual analogue scale)

